## 9.6 Stopping rules:

## 9.6.1 Part 1 (completed)

The study will be stopped according to the following rules:

- 1. The study will stop early for safety if the first three entered participants in Zone 1 experience DLT on combinations in Zone 1 in Stage 1.
- 2. If at any point in Stage 2, the set of acceptable combinations is empty, the trial will stop for safety.
- 3. The study will stop if the recommendation is to assign the next participant to a combination that already has 20 participants treated at that combination.

#### 9.6.2 Part 2

Safety will be assessed by monitoring the number of participants who experience a DLT. In Part 1, 1/16 (6.3%, 95%Cl [0.2, 30.2%]) participants treated on Arm E experienced a DLT. For Part 2 the upper boundary of a sequential probability ratio test (SPRT) based upon a binomial test of proportions for DLT will be used for monitoring to protect against excessive DLT rates. The stopping boundary is for a SPRT contrasting a 5% versus 30% DLT rate, with nominal type I and II errors of 5% and 20%, respectively. Safety stopping guidelines for the occurrence of DLTs are detailed in the following table. If a stopping bound is crossed then accrual to the study will be suspended until the study PI, co-investigators and the DSMC can review the data, and determine if the study should continue, be amended or be closed to further accrual.

Version Date: 07-31-17

Table 21: Incidence of Treatment-Related DLTs

Incidence of treatment related DLTs					
Number of participants   Stopping boundary					
2-4	≥2				
5-11	≥3				
12-18	≥ 4				

#### 9.7 Analyses

### 9.7.1 Safety:

All participants who receive any study intervention will be monitored for adverse events. Adverse events will be described and coded based upon the NCI CTCAE v4.03. A DLT is defined as any unexpected adverse event that is possibly, probably or definitely related to treatment and satisfies the criteria in section 7.8. Occurrence of DLTs will guide escalation and stopping decisions. At study conclusion frequency, proportion and severity of adverse events, and DLTs by arm will be tabulated.

# 9.7.2 Immunologic response:

Subjects are evaluable for immune response if at least one post treatment sample is measurable for response. Peak immunogenicity will be evaluated by direct Elspot assay against the defined nonamer peptides in the peripheral blood. The presence or absence of an immune response will be defined by induction of at least a 2-fold increase in IFN-gamma-secreting cells over background, and over pre-existing responses, and at least 30 IFN-gamma secreting spots per 100,000 CD8 T cells, as described . This assessment will be performed on blood through week 12, although a minimum of 4 weeks of data will be used to guide decisions about the range of optimal dose combinations. IRR is defined as the proportion of participants where presence (as defined above) of an immune response has been observed.

Durable immunogenicity will be evaluated week 26 by Ellspot assay against the defined nonamer peptides in the peripheral blood. The presence or absence of an immune response at that time will be defined by induction of at least a 2-fold increase in IFN-gamma-secreting cells over background, and over pre-existing responses, and at least 30 IFN-gamma secreting spots per 100,000 CD8 T cells, as described . This assessment will be performed on blood through week 26.

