Tyrosinase is an enzyme involved with melanin synthesis. Epitopes derived from tyrosinase have been identified for HLA-A1, HLA-A2, and other class I alleles 26. In the proposed study, we are including long peptides incorporating one epitope (DAEKSDICTDEY) restricted by HLA-A1 and one epitope (YMDGTMSQV) restricted by HLA-A2. The parent epitope of tyrosinase240-251, DAEKCDICTDEY, has been modified to incorporate a serine residue at position 244 of the peptide (DAEKSDICTDEY). This modification prevents disulfide bond formation within the peptide, but does not interfere with HLA-A1 binding or with T cell recognition . In phase II clinical trials conducted by the UVA HITC (UVA-Mel31, Mel36, Mel39, Mel43, and Mel44), immunological responses against the DAEKSDICTDEY peptide were detected as the dominant peptide target for participants who expressed HLA-A1 and who were immunized with a synthetic peptide mixture containing the DAEKSDICTDEY peptide. CTL cultured from a vaccine draining node (sentinel immunized node, SIN) after vaccination with DAEKSDICTDEY were capable of lysing HLA-A1+ tumor cells naturally expressing tyrosinase. The naturally occurring HLA-A2 restricted epitope from tyrosinase, tyrosinase369-377 YMDGTMSQV, contains a post-translational modification of an asparagine to aspartic acid at residue 371 38. In phase II clinical trials conducted by the UVA HITC, immunological responses to the YMDGTMSQV peptide have been detected frequently in stage III and IV melanoma participants who expressed HLA-A2, and were immunized with a synthetic peptide mixture containing this peptide 12;31-34.

MAGE-A1 and MAGE-A10 are members of the MAGE gene family and are expressed in the testes, as well as in several different tumor types such as melanoma, breast, prostate, esophagus, colon, and lung . One epitope derived from MAGE-A1 (SLFRAVITK) is included in the proposed study. The MAGE-A196-104 epitope (SLFRAVITK) was identified by Chaux et al. , and was first tested in humans in UVA-Mel39, in which immunogenicity and safety have been demonstrated . It is a highly immunogenic peptide in the Mel39, Mel43, and Mel44 trials .

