# 4.1 Inclusion Criteria

4.1.1 Histologically or cytologically proven Stage IIB-IV melanoma (at diagnosis or at the time of recurrence) rendered clinically free of disease by surgery, other therapy, or spontaneous remission within 6 months prior to registration; patients with treated brain metastases may be eligible if they meet the criteria in 4.1.4. Small radiologic or clinical findings of an indeterminate nature will not be a basis for exclusion, and brain metastases treated in accord with section 4.1.4 will not be a basis for exclusion.

Staging of cutaneous melanoma will be based on the 7th edition AJCC staging system (Appendix 2).

Version Date: 07-31-17

Staging of mucosal melanomas will be based on the following system modified from the cutaneous melanoma staging system: 2.01- 4mm primary with ulceration or > 4mm primary= stage IIB, lymph node metastases = stage III, distant metastases = stage IV.

- 4.1.2 Patients may have had multiple primary melanomas.
- 4.1.3 Patients may have had or may have a metastasis from a cutaneous primary site, mucosal primary site, or unknown primary site.
- 4.1.4 Patients with brain metastases may be eligible if all of the following are true:
  - The total number of brain metastases ever is less than or equal to 3.
  - The brain metastases have been completely removed by surgery or have been treated completely by stereotactic radiotherapy. Stereotactic radiotherapy, such as gamma knife, can be used up to 1 week prior to study entry. In the absence of concerning clinical findings, repeat scans are not required after stereotactic radiotherapy if the patient enrolls within 8 weeks of completing the stereotactic therapy.
  - There has been no evident growth of any brain metastasis since treatment.
  - No treated brain metastasis is greater than 2 cm in diameter at the time of protocol entry.
- 4.1.5 Patients must have at least one axillary and/or inguinal lymph node basin that is intact (no prior excisional biopsy of a node or complete lymph node dissection).
- 4.1.6 All patients must have:
  - ECOG performance status of 0 or 1.
  - Ability and willingness to give informed consent.
- 4.1.7 Laboratory parameters as follows:
  - 1) HLA-A1, A2, A3, B35, or B51.
  - 2) ANC > 1000/mm^3, and Platelets > 100,000/mm^3 and Hgb > 9 g/dL

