# 6.0 CLINICAL AND LABORATORY EVALUATION

#### 6.1 Screening

The following studies should be completed within 6 weeks prior to randomization unless otherwise noted:

- 6.1.1 Class I HLA-typing (any time prior to randomization; typing for HLA-A and HLA-B is sufficient). If the patient is known to express HLA-A1, A2, or A3, HLA-B testing is not required).
- 6.1.2 Review of pathology at the treating and participating institution (any time prior to randomization). Central pathology review at UVA is not required for pathology reviewed at other participating institutions.
- 6.1.3 CBC with differential, including automated lymphocyte count if available (0.3 ml)
- 6.1.4 Comprehensive chemistry panel to include sodium, potassium, creatinine, fasting glucose, calcium, total bilirubin, AST, ALT, and alkaline phosphatase. NOTE: fasting blood sugars may be evaluated 4h or more after last eating (0.9 ml)
- 6.1.5 Lactate Dehydrogenase (LDH) (0.3 ml)
- 6.1.6 Urinalysis
- 6.1.7 β-HCG for women of childbearing potential (within two weeks prior to randomization)

Version Date: 07-31-17

- 6.1.8 HgB-A1C (only required at baseline)
- 6.1.9 HIV and HCV screening (within 6 months prior to randomization)
- 6.1.10 Chest x-ray or chest CT, abdominal and pelvic CT, and head CT or MRI. PET/CT fusion scan may replace scans of the chest, abdomen, and pelvis.
- 6.1.11 Complete history and physical examination, including:
  - Vital signs
  - Weight
  - Performance Status
  - Assessment of skin and nodal basins for evidence of disease recurrence or metastasis
  - Designation of vaccination sites
  - Medication review

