## 8.0 EVALUATION OF IMMUNOLOGIC RESULTS

A primary goal is to evaluate immunogenicity of LPV7 in each of 7 adjuvant preparations, including IFA, with or without TLR agonists. The primary immunological response of interest is the CD8+ T cell response to the defined minimal peptides epitopes contained within each of the 7 long peptides (Table 2). This will be assessed primarily by Elspot assay as outlined below. Associated analyses will include the durable immune response (week 26), and the peak magnitude of the CD8+ T cell responses. Details related to study design are in Section 9.

Studies in the peripheral blood will also assess CD4 T cell responses, T cell persistence, antibody response, Th1/Tc1 deviation and cytokine functionality. The antitumor immune response to vaccination with LPV7 with TLR agonists will be compared to vaccination with

Version Date: 07-31-17

IFA alone, and the highest immune response rate will be selected. Blood will be collected as described in Section 6.

Skin biopsy specimens from the vaccine sites after 1 (day 8) and 3 vaccines (day 22) (and from normal skin controls) will be evaluated for changes induced by TLR agonists, and these will be evaluated as we have for a prior study  $^{50}$ : immunohistochemistry of the vaccine-site immune cells to define the cell types and function; multiparameter flow cytometry to identify activation status of antigen specific cells, regulatory T cells, and MDSC; ELIspot assays for the ability to produce IFN $\gamma$ ; and Luminex studies to define the cytokine and chemokine profiles of the VSME.

The following laboratory criteria will be used to evaluate effects of the vaccines and the TLR agonists in circulating peripheral blood mononuclear cells (PBMC) and in the vaccine sites. In general, immunological evaluations will be performed in batch.

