#### 8.2 ELlspot assav

We will evaluate CD4+ and CD8+ T cell responses in the peripheral blood using a direct (ex vivo)  $\Box$  Ispot assay for IFN $\gamma$  as reported. This will be performed in a core laboratory dedicated to immune monitoring, and with SOPs, controls, and quality assurance measures, which we have reported. Vaccination site infiltrating lymphocytes will be evaluated by  $\Box$  Ispot as well. Vaccine site infiltrating lymphocytes will be compared to those in peripheral blood.  $\Box$  Ispot assays after one in vitro stimulation (stimulated  $\Box$  Ispot) may also be employed if appropriate, as reported  $\Box$ 

 $\underline{\text{CD4+ T cell responses}}$  will be assessed by IFNY  $\underline{\text{EL}}$  lspot assay using the mixture of 7 long peptides and also pools of 15-mer peptides (overlapping by 5 residues) from each peptide (4 peptides for each long peptide) as antigen sources.

Durability of CD8 and helper T cell responses will be assessed by measuring T cell activity at 26 weeks, and for longer intervals when available, with the hypothesis that there will be increased durability of T cell responses when compared to prior experience with short peptides and will be improved with TLR agonists when compared to IFA alone in this study.

We have extensive stores of cryopreserved T cells reactive to minimal epitope peptides included in the 12 short peptides (12MP) mixture, and detectable by IFN-gamma ELIspot assay 8;12 and by cytotoxicity assays. These cells will serve as positive controls for reactivity to the minimal epitopes contained within the long peptides used in this trial.

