#### 9.7.3 At study conclusion:

Frequency and magnitude of adverse events will be summarized by arm. Point estimates and confidence intervals will be calculated for all dichotomous endpoints. If more than one combination is contained within the range of optimal combinations, estimates and confidence intervals will be used to estimate the difference in IRR between pairs of combinations among those in the range of optimal combinations.

Immunogenicity will be evaluated by direct Elspot assay against the defined nonamer peptides in vaccine site biopsies using the above criteria. Disease-free survival is defined as the duration of time from start of treatment to time of recurrence/progression or death from any cause, whichever occurs first. Participants who do not experience an event (recurrence/progression or death) will be censored at date of last contact. Overall survival is defined as the duration of time from start of treatment to time of death from any cause. Participants who do not experience an event (death) will be censored at date of last contact.

Version Date: 07-31-17

Disease-free survival and overall survival distributions will be estimated by the product limit method of Kaplan and Meier.

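### Does testing immune response against nonamer peptides leave the HLA-A1 12-mer out of the endpoint?

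*Combined protocol and SAP*

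**What the plan says.** The statistical section names the test peptides three times, each time as nonamers:

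- Peak response, 9.7.2: "Peak immunogenicity will be evaluated by direct Elspot assay against the defined nonamer peptides in the peripheral blood".
- Durable response, 9.7.2: "Durable immunogenicity will be evaluated week 26 by Ellspot assay against the defined nonamer peptides in the peripheral blood".
- Vaccine site, 9.7.3: "Immunogenicity will be evaluated by direct Elspot assay against the defined nonamer peptides in vaccine site biopsies using the above criteria".

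Section 8.0, which defines the primary immunologic outcome, describes the target differently, as the "CD8+ T cell response to the defined minimal peptides epitopes contained within each of the 7 long peptides", with a reference to Table 2. Section 8.2 plans cryopreserved T cells as "positive controls for reactivity to the minimal epitopes contained within the long peptides used in this trial". Section 1.2.2 describes "long peptides incorporating one epitope (DAEKSDICTDEY) restricted by HLA-A1", and Table 2 lists no other HLA-A1 epitope.

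The HLA entry criterion in 4.1.7 is "HLA-A1, A2, A3, B35, or B51". Screening section 6.1.1 adds: "If the patient is known to express HLA-A1, A2, or A3, HLA-B testing is not required". Under 9.7.2 a participant is evaluable with one measurable sample after treatment; HLA type plays no part.

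**The concern.** A nonamer has nine residues, and the HLA-A1 epitope has twelve. Taken at its word, 9.7.2 would drop the only peptide in the vaccine chosen for HLA-A1. Section 1.2.2 says this peptide was the dominant target in HLA-A1 participants in earlier trials by the same group.

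A patient can enrol on HLA-A1 alone, need not be typed for HLA-B, and stays in the denominator of the immune response rate. Under the strict reading, a participant with A1 and none of the other four alleles would be counted with no matched test peptide, almost certainly as a non-responder. The response rate would be pulled down, and the Part 2 benchmark of 12 responders in 16 (9.5.2) would be harder to reach. Because that benchmark is presented as twice Arm E's 6/16, a panel that differed between the two parts would also distort the comparison.

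**Working it through.** **1. Count the residues.** Sequences and positions are from Table 2; length = last position − first position + 1.

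| Allele | Minimal epitope | Positions | Length |
|---|---|---|---|
| A1 | DAEKSDICTDEY | 240–251 | 12 |
| A2 | YMDGTMSQV | 369–377 | 9 |
| A2 | IMDQVPFSV | 209–217 | 9 |
| A2 | GLYDGMEHL | 254–262 | 9 |
| A3 | ALLAVGATK | 17–25 | 9 |
| A3 | SLFRAVITK | 96–104 | 9 |
| B35/B51 | MPFATPMEA | 94–102 | 9 |

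The mismatch is real: six nonamers and one 12-mer.

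**2. Ask which set the plan intends.**

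- Section 8.0 is explicit. It covers each of the seven long peptides and names ELIspot as the main assay. Six epitopes cannot satisfy it.
- Section 9.7.2 takes its criterion (2-fold rise, at least 30 spots per 100,000 CD8 cells) from reference 34, the randomized trial of helper peptides and cyclophosphamide with the multipeptide vaccine. Section 1.2.2 cites that report among those in which responses to DAEKSDICTDEY were detected.
- The control cells in 8.2 are reactive to epitopes from the 12-short-peptide mixture, and 1.2.2 lists DAEKSDICTDEY among the peptides carried over from it. This is supporting evidence only: planned controls do not prove which panel is run, and that mixture is not the source of the NY-ESO-1 epitope.
- No section says that the 12-mer is left out, or that a shortened form replaces it.

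**3. Reproduce the figures that rest on the endpoint (9.5.2), by exact Clopper–Pearson limits.**

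- 12/16, one-sided 80% lower limit: 0.20 quantile of Beta(12, 5) = 0.615. Stated: 61.5%.
- 6/16, 90% interval: 0.05 quantile of Beta(6, 11) = 0.178 and 0.95 quantile of Beta(7, 10) = 0.609. Stated: 17.8% to 60.9%.
- Accrual: 16 / 0.90 = 17.8, rounded up to 18. Stated: 18.

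These depend only on counts and are the same under either wording.

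**4. Size the harm if the strict reading were applied.** Let m be the number of the 16 with A1 and none of A2, A3, B35 or B51. The documents do not give m, so 0, 1 and 2 are assumed. Count these m as non-responders and let p be the true response rate among the rest. Then P(at least 12 of 16) = P(X ≥ 12) with X ~ Binomial(16 − m, p).

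| m | Rate needed, 12/(16 − m) | p = 0.75 | p = 0.85 |
|---|---|---|---|
| 0 | 75% | 0.63 | 0.92 |
| 1 | 80% | 0.46 | 0.82 |
| 2 | 86% | 0.28 | 0.65 |

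The drop is large, but it needs two things that the documents do not supply: omission of the 12-mer, and m above zero. Nor is m simply the number of participants who enrol as A1 without A2 or A3. Not being typed for HLA-B does not make a participant B35- or B51-negative, and no section restricts the assay to typed alleles, so an untyped carrier could still respond to the NY-ESO-1 nonamer.

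**5. Check the comparison with Arm E.** Suppose one panel served both parts and a share s of each group had no matched peptide. The two rates become (1 − s)r₁ and (1 − s)r₂, and their ratio is still r₂/r₁. The 12/16 mark was set as 2 × 6/16 on whatever panel Part 1 used, so a common panel keeps the doubling like for like unless s differs between the groups. Only a switch of panel between parts would break this, and nothing in the documents suggests one.

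**The case for a change.** The best argument for a change is that 9.7.2 is the text that defines response and the response rate, and an analyst should not have to correct it from section 8. The protocol also uses the term accurately elsewhere: section 1.2.2 applies it to the nine-residue NY-ESO-1 epitope. The wording recurs in three endpoint definitions, the edit would cost almost nothing, and the operational assay detail sits in a Study Manual that is not among these documents.

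Part of this stands. The term is inexact in all three places, and the documents cannot prove which peptides were plated for Arm E. It is also right that Arm E and E2 must be scored on the same peptides, but that is true of any comparison between them and does not depend on this word.

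The step from inexact term to faulty endpoint does not stand. Section 8.0 is an operative definition of the primary response, names all seven peptides and cites the table. The two sections conflict only if nonamer is taken as a deliberate restriction, and nothing supports that. The tetramer list in 8.3 adds little: it covers only the A2 and A3 epitopes, so it omits B35/B51 as well as A1, and 8.3 itself keeps ELIspot as the primary measure. Rewriting the three sentences would leave the assay, the counts and the decision rule where they are.

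**Conclusion.** This is a clerical slip: nonamer stands in for minimal epitope, and it misdescribes one peptide of seven. Read as a whole, the plan includes the HLA-A1 12-mer, and a competent analyst working from 8.0 and Table 2 would include it. The effect on stated figures is nil: 16 eligible, 18 accrued, 6/16 and 12/16 with their limits all reproduce.

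The falls in the chance of reaching 12/16 shown in the working are conditional on an omission that no document reports and on assumed values of m, so they do not measure a defect in this plan. Missing 12/16 would in any case lead only to further study under 9.5.2. The conclusion assumes that the laboratory panel follows 8.0 and is the same for Arm E and E2. The documents point that way but cannot confirm it. No change to the plan is called for.

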#### 9.7.3 At study conclusion:

Frequency and magnitude of adverse events will be summarized by arm. Point estimates and confidence intervals will be calculated for all dichotomous endpoints. If more than one combination is contained within the range of optimal combinations, estimates and confidence intervals will be used to estimate the difference in IRR between pairs of combinations among those in the range of optimal combinations.

Immunogenicity will be evaluated by direct Elspot assay against the defined nonamer peptides in vaccine site biopsies using the above criteria. Disease-free survival is defined as the duration of time from start of treatment to time of recurrence/progression or death from any cause, whichever occurs first. Participants who do not experience an event (recurrence/progression or death) will be censored at date of last contact. Overall survival is defined as the duration of time from start of treatment to time of death from any cause. Participants who do not experience an event (death) will be censored at date of last contact.

Version Date: 07-31-17

Disease-free survival and overall survival distributions will be estimated by the product limit method of Kaplan and Meier.

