# 4.4.3 Management of Participants

This study will be conducted on an outpatient basis, with participants scheduled to be evaluated on days 1, 8, 15, 22, 36, 43, 57, 78, and 85, and week 26 (or more often if needed for testing or medical reasons). As needed, there may also be follow-up within 1-3 weeks after biopsies performed on days 8 or 22 for wound evaluation. Participants will also be followed-up at 52 weeks (1 year) and at 2 years with blood draws for studies of immune response durability. During off treatment follow-up, participants will be followed yearly for survival and disease status.

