# 5.5.4 Delayed Visit for Reasons Other Than Toxicity

A schedule for return visits should be established at the first visit. If a participant misses a treatment, the missed treatment will be administered as soon as possible, so that the subsequent vaccinations are given in the appropriate intervals. Treatment may be continued for an additional time period, if needed. Participants who are vaccinated outside of the established schedule should return to the original schedule as soon as possible.

The table below defines what constitutes a delayed visit, whether the participant should continue to be treated, and whether a protocol violation/deviation should be reported and recorded. The range of days is counted from the original scheduled date.

Table 6. Delayed Visit for Reasons other than Toxicity				
Treatment Period	Range of Days	Participant Treatment	Protocol Deviation	
Vaccine 1				
Day 1	± 2 days	Vaccine/Labs	No	
	± 3 to 7 days	Vaccine/Labs	Yes	
	± 8 or more days	Labs	Yes	
Vaccine 2/Biopsy*				
Day 8	± 2 days	Vaccine/Labs/Biopsy	No	
	± 3 to 7 days	Vaccine/Labs/Biopsy	Yes	
	± 8 or more days	Labs	Yes	
Vaccine 3*				
Day 15	± 2 days	Vaccine/Labs	No	
	± 3 to 7 days	Vaccine/Labs	Yes	

	± 8 or more days	Labs	Yes
Assessment/Biopsy			
Day 22	± 2 days	Biopsy/Labs	No
	± 3 to 7 days	Biopsy/Labs	Yes
	± 8 or more days	Labs	Yes
Assessment			
Day 43	L O dovo	Labs	No
	± 2 days	1 1 1	
	± 3 to 7 days	Labs	Yes
	± 8 or more days	Labs	Yes
Vaccines 4-6*			
Days 36, 57, 78	± 7 days	Vaccine/Labs	No
	± 8 to 14 days	Vaccine/Labs	Yes
	± 15 or more days	Labs	Yes
Assessment			
Day 85 (Week 12)	± 7 days	Labs/Scans	No
	± 8 to 14 days	Labs/Scans	Yes
	± 15 or more days	Labs	Yes
Follow-up			
Week 26, Year 1 and 2	± 7 days	Scans/Labs	No
	± 8 to 30 days	Scans/Labs	Yes

A participant will be taken off protocol treatment if more than one vaccination is delayed [ $\pm$  3 to 7 days] during the treatment period.

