## 6.2.11 Weeks 52 and 104 (Year 1 and 2)

- Interval history and physical examination directed at new signs and symptoms. Examination of the vaccine site(s) should be included.
- Vital signs
- Weight
- Performance status
- Medication review
- Blood collection for immunologic testing: The following blood samples for research will be provided to UVA and processed by the UVA BTRF and stored by the UVA-HITC IML:
  - o 80 cc blood collected in heparinized green top tubes for lymphocytes.
  - o 20 cc blood collected in red top tubes for serum

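### DFS is censored at last contact with no requirement that disease status was assessed then, so DFS may be overstated for any participant whose last contact was survival-only

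*Combined protocol and SAP*

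**What the plan says.** Section 9.7.3 defines the endpoint: "Disease-free survival is defined as the duration of time from start of treatment to time of recurrence/progression or death from any cause, whichever occurs first". Its censoring rule is: "Participants who do not experience an event (recurrence/progression or death) will be censored at date of last contact". The OS rule is parallel: "Participants who do not experience an event (death) will be censored at date of last contact". The analysis is descriptive: "Disease-free survival and overall survival distributions will be estimated by the product limit method of Kaplan and Meier". The Precis ranks both endpoints as exploratory and says the study is not powered for clinical outcome.

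On how recurrence would be found during follow-up:

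- Section 4.4.3: "During off treatment follow-up, participants will be followed yearly for survival and disease status". No method is given.
- Section 7.4.2: participants who receive additional treatment are followed yearly for progression and survival.
- Section 6.2.11 (weeks 52 and 104): "Interval history and physical examination directed at new signs and symptoms", with vital signs, weight, performance status, medication review and research blood. No imaging is listed.
- Appendix 1: history and physical marked at days 365 and 730; chest imaging marked only pre-study and at days 85 and 183.
- Section 5.5.4, Table 6: the follow-up row labelled "Week 26, Year 1 and 2" gives scans and labs as the activity.

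**The concern.** Last contact is the right censoring date for death, because any contact establishes that the participant is alive. For DFS the participant must also be known to be free of recurrence on that date. If the last contact recorded survival only, the time since the last disease assessment is counted as disease-free with nothing behind it. A recurrence in that interval is missed and the Kaplan-Meier curve is pushed up.

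No test, sample size or decision rule rests on DFS. The Precis does say that trends in clinical outcome will be read alongside the immunologic data when judging which vaccination strategy to take forward, so the curve should mean what its label says.

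The disagreement about scans at years 1 and 2 is a second, separate matter. It affects which recurrences can be detected, whatever the censoring date. Table 6 also defines protocol deviations, so it is unclear whether a year 1 visit without a scan complies.

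**Working it through.** **No plan figure to reproduce.** The documents give no DFS rate, event count, hazard ratio or power. The check is therefore of direction and possible size, and every DFS rate below is an assumption.

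**Step 1. When the two censoring dates differ.** If disease status is ascertained at the last contact, last contact and last assessment are the same date and the rules coincide. They differ only when the last contact was survival-only.

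**Step 2. Size when assessment stops but contact continues.** Suppose a share f has no disease assessment after week 26 (month 6) and is censored at a survival-only contact after month 24. Their recurrences after month 6 go uncounted, so their apparent 24-month DFS is S(6). Deaths are ignored. Then

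- apparent S(24) = (1 − f) × S(24) + f × S(6)
- bias = f × [S(6) − S(24)]

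With exponential recurrence, S(6) = S(24)^(6/24).

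| True S(24) | S(6) | S(6) − S(24) | Bias, f = 10% | f = 25% | f = 50% |
|---|---|---|---|---|---|
| 50% | 84.1% | 34.1 points | 3.4 | 8.5 | 17.0 |
| 60% | 88.0% | 28.0 points | 2.8 | 7.0 | 14.0 |
| 70% | 91.5% | 21.5 points | 2.1 | 5.4 | 10.7 |

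Censoring these participants at their last disease assessment brings the bias to zero, provided that loss of assessment is unrelated to recurrence risk.

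For scale, take the 16 eligible participants planned for Part 2. One affected participant is f = 1/16 = 6.25%, and at a true 50% the bias is 0.0625 × 34.1 = 2.1 points. The standard error of an uncensored 50% proportion in 16 participants is √(0.5 × 0.5/16) = 12.5 points.

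**Step 3. When assessments stay on schedule.** A Kaplan-Meier simulation used 200,000 participants per scenario. It assumed true 24-month DFS of 50, 60 or 70%, last contact uniform on 12 to 48 months, and 0, 25 or 50% of recurrences occult without imaging (evident after a mean of 12 months). Scans after week 26 were either absent or done at years 1 and 2, and the final contact was either survival-only or included disease status. That gives 3 × 3 × 2 × 2 = 36 scenarios. The 24-month difference between the two censoring rules was 0.000 in all of them. This follows from the set-up: with assessments on a common schedule, a survival-only contact between two visits leaves the same people at risk at each visit.

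**Step 4. Imaging, kept apart.** With no scans after week 26, a survival-only final contact and 25 to 50% of recurrences occult, estimated 24-month DFS was:

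- 54.4 to 58.2% against a true 50%
- 63.6 to 66.9% against 60%
- 72.6 to 75.4% against 70%

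The figures were the same under either censoring rule. With scans at years 1 and 2 and a survival-only final contact, the error was within 0.3 points. When the final contact did ascertain disease status, estimates ran from about 3 points below the truth to about 5 above, again the same under both rules. The censoring date does not repair what missed imaging does.

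**The case against.** The strongest reply is that the plan describes follow-up that does collect disease information. Sections 4.4.3 and 7.4.2 make yearly follow-up cover disease status or progression, a history and physical is scheduled at weeks 52 and 104, and an Appendix 1 footnote calls for fuller staging on new liver enzyme or LDH abnormalities or chest x-ray nodules. On that description last contact and last assessment largely coincide.

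Most of this stands. A reader might infer from the rule that DFS is overstated. The documents do not show that: no share of survival-only last contacts is given, and Step 3 finds no difference when assessments stay on schedule. A reader might also infer that about 12 months per event-free participant goes unassessed. That requires the yearly contact to be survival-only, contrary to what 4.4.3 and 7.4.2 say it is for.

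What the reply does not settle is that intended follow-up is not a censoring rule. Neither section says how disease status is established. In Appendix 1 the laboratory tests that could trigger fuller staging end at day 85 and chest imaging ends at day 183, so no scheduled trigger remains after week 26. A survival-only last contact is possible, and section 9.7.3 would accept it.

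On imaging, it is fair to say that Table 6 sets visit windows and uses loose labels. It pairs vaccine with labs on days 15, 36 and 57, when sections 6.2.3, 6.2.5 and 6.2.7 and Appendix 1 schedule no blood draw. Its follow-up row pools week 26, which does have chest imaging, with years 1 and 2. The scan entry may be a labelling slip, but it still disagrees with the other two places.

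**Conclusion.** The concern holds in a limited form. Section 9.7.3 lets a contact without disease assessment extend disease-free time. DFS may therefore be overstated for participants whose last contact was survival-only, by an amount the documents do not determine. The 2.1 to 17.0 points in Step 2 rest wholly on assumed values: 10 to 50% without assessment after week 26, exponential recurrence, true 24-month DFS of 50 to 70%, and no deaths. Where every last contact carries a disease assessment, the bias from the censoring rule is zero. With an exploratory, unpowered endpoint and only Kaplan-Meier estimation planned, this is a minor point.

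The year 1 and 2 scan entry is a schedule inconsistency in its own right. A reader might infer from it that DFS in Part 1 and Part 2 would not be comparable. The documents do not support that: nothing says the two parts follow different imaging schedules, no DFS comparison between them is planned, and the Part 2 conclusion in section 9.5.2 rests on immune response.

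**What to change.** 1. In section 9.7.3, censor event-free participants for DFS at the last date they were documented free of disease by clinical or radiologic assessment, and state what counts as such an assessment. Keep last contact for OS.
2. Separately, reconcile Table 6 with section 6.2.11 and Appendix 1 on scans at years 1 and 2. This review takes no view on which entry is right.

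The first change is a sentence or two in the analysis section. Its cost is some shortened DFS follow-up, plus a check that the case report form captures the date of each disease assessment, which the documents do not state. The second may be a label correction only, but if the schedule itself changes it could add or remove a procedure.
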